**Effect of Upper Airway Stimulation on Cardiovascular Dysfunction in Obstructive
Sleep Apnea**

Protocol Version 2.0, dated 10/6/2016

NCT03051165

1. Title Page

Full Study Title

Effect of Upper Airway Stimulation on Cardiovascular Dysfunction in Obstructive Sleep Apnea

Short Study Title

UAS on CV Dysfunction in OSA

Principal Investigator

[name] MS
Assistant Professor
Department of Otolaryngology

Sponsors

None

Protocol Version Number & Version Date

Version 2.0 | 10/6/2016

2. External collaborators

None

3. Abstract

The prevalence of obstructive sleep apnea (OSA) is significant and increasing with greater obesity and aging of populations. Patients with moderate-severe OSA carry excessive risk of cardiovascular sequelae compared to controls. The first-line treatment for OSA, positive airway pressure, has demonstrated dramatic reduction in cardiovascular risk; however, long-term acceptance of this therapy approaches 50%. The advent of hypoglossal nerve stimulation (HGNS) therapy has provided a promising option to a subgroup of patients with moderate-severe OSA. This therapy has demonstrated long-term improvement in polysomnographic and quality of life measurements with adherence rates greater than 80%. The effect of HGNS on mitigation of cardiovascular risk in this vulnerable population, however, is entirely unknown.

The cardiovascular risk from moderate-severe OSA is intimately related to sympathovascular dysfunction. Multiple methods are available to capture various elements of this physiologic process including peripheral arterial tonometry (PAT), flow mediated dilation, peripheral arterial stiffness, ambulatory blood pressure monitor, dysrhythmia monitor and serum biomarkers. Using our prospective cohort of moderate-severe OSA patients undergoing HGNS, we will evaluate the effects of hypoglossal nerve stimulation on the sympathetic nervous system. The outcome of this study will

provide a potential mechanism for cardiovascular risk reduction for this novel, physiologic therapy for OSA.

4. Introduction & Background

Obstructive sleep apnea (OSA), repetitive collapse of the upper airway during sleep, represents a growing individual and public health concern. This disease negatively impacts patients' sleep quality and daytime function, including 3-10 fold increased risk of motor vehicle accidents. Several large, longitudinal cohorts have consistently demonstrated deleterious effects of OSA on cardiovascular health, including elevated rates of incident hypertension, myocardial infarction and cerebrovascular accidents. The link between OSA and cardiovascular consequences can be largely explained by autonomic imbalance during repeated episodes of nocturnal airway obstruction. Compared to controls, patients with OSA have increased sympathetic activity when awake, with further elevation of both sympathetic activity and blood pressure during sleep. Multiple physiologic mechanisms are responsible for these autonomic changes during obstructive episodes including the interaction of baroreceptors, chemoreceptors and respiratory afferent receptors. Positive airway pressure (PAP) serves as a pneumatic stent for the airway, maintaining airway patency and normoxia. PAP therapy has demonstrated consistent, meaningful reductions in sympathetic overactivity during wake and sleep.

Though PAP therapy is highly efficacious, fewer than 50% of patients are adequately treated due to adherence difficulty. In 2014, the Federal Drug Administration approved hypoglossal nerve stimulation (HGNS) for the treatment of patients with moderate-severe OSA unable to adequately use PAP. Recently published three-year data for this therapy demonstrated stable, marked improvement in key polysomnography indices, sleepiness measures and functional outcomes with adherence greater than 80%. To date, however, no study has examined cardiovascular endpoints of HGNS therapy in OSA patients.

Our overarching aim is to evaluate the effect of HGNS therapy on autonomic and vascular function as measured by changes in peripheral arterial tonometry, flow mediated dilation, peripheral arterial stiffness, 24-hour ambulatory blood pressure, 7-day dysrhythmia monitor and serum biomarkers before, during and after treatment in this high-risk cardiovascular population. **We hypothesize that all aforementioned measurements will be significantly improved following HGNS therapy and return to baseline values following a therapy withdrawal period.**

5. Objectives

Aim 1

Determine the impact of upper airway stimulation on peripheral arterial tonometry ratio related to obstructive episodes in this cohort of patients with moderate-severe obstructive sleep apnea

Hypothesis: The peripheral arterial tonometry ratio related to obstructive episodes will be improved with increasing levels of upper airway stimulation

Aim 2a

Determine the impact of upper airway stimulation on flow mediated dilation in this cohort of patients with moderate-severe obstructive sleep apnea

Hypothesis: The flow mediated dilation parameters will be improved at therapeutic levels of upper airway stimulation and returned to pre-operative levels after 30-day withdrawal period

Aim 2b

Determine the impact of upper airway stimulation on peripheral arterial stiffness in this cohort of patients with moderate-severe obstructive sleep apnea

Hypothesis: The peripheral arterial stiffness parameters will be improved at therapeutic levels of upper airway stimulation and returned to pre-operative levels after 30-day withdrawal period

Aim 2c

Determine the impact of upper airway stimulation on 24-hour ambulatory blood pressure in this cohort of patients with moderate-severe obstructive sleep apnea

Hypothesis: The 24-hour ambulatory blood pressure will be improved at therapeutic levels of upper airway stimulation and returned to pre-operative levels after 30-day withdrawal period

Aim 2d

Determine the impact of upper airway stimulation on serum biomarker profile in this cohort of patients with moderate-severe obstructive sleep apnea

Hypothesis: The serum biomarker profile will be improved at therapeutic levels of upper airway stimulation and returned to pre-operative levels after 30-day withdrawal period

6. Study Design and Methods

Each participant will undergo three sets of blood testing. Each set of testing will require travel to the Emory Clinical Cardiovascular Research Institute (ECCRI) facility at Woodruff Memorial Research Building on Clifton Campus. The subjects will be provided directions, lunch and parking vouchers for each visit. The subject will be registered at the EECRI facility each time and undergo fasting bloodwork.

Study Timeline

- Post-operative appointment: obtain consent for study enrollment (Day 1)
- WatchPAT baseline home sleep test (Night 1)
- Baseline 24-hour ambulatory blood pressure monitoring (Day 2-3)
- Baseline serum biomarkers/vascular testing (Day 15)
- Device Activation (Day 15)
- In-lab Polysomnography Titration (Day 45)
- WatchPAT treatment home sleep test (Night 75)
- Clinic visit (Day 105)

- Treatment serum biomarkers/vascular testing, 24-hour ambulatory blood pressure monitoring (Day 105-106)
- Therapy Withdrawal (Day 106-135)
- WatchPAT withdrawal home sleep test (Night 135)
- Withdrawal serum biomarkers/vascular testing, 24-hour ambulatory blood pressure monitoring (Day 136-137)
- Therapy Reactivation (Day 137)

Risks

The risks from participating in the research include the release of confidential information.

Due to the research nature of this study there may be other risks that are currently unknown. For instance, in the future it may be possible to link genetic factors to medical problems that could possibly influence insurability and employability, either for yourself or for your immediate family. To prevent this from being a problem for you in the future, your blood samples and research results will be labeled with a study ID number and not your name. Therefore, there will be no direct linkage between your blood sample and your name. However, this code will allow researchers to link your clinical information with your blood sample, without knowing your name.

Blood testing and genetic testing: rarely, bleeding can occur around the site where we draw your blood. This is not dangerous, but, if it occurs, it could result in a small bruise. Skin tape reactions may occur in a small portion of allergic subjects, but generally well tolerated and causes no long-term side effects.

Blood flow measurements: The blood pressure inflation lasts for 5 minutes and can result in temporary feelings of numbness and pins and needles in the arm that last for one or two minutes. However, this is generally well tolerated and causes no long-term side effects. The blood flow measurement device worn for 24 hours is very well tolerated. The device is light weight and padded and does not disturb sleep or any other daily activities.

Sleep testing: The wearing of the sleep test device may result in decreased sleep quality for the night of testing.

Benefits

This study is not designed to benefit you directly. Your obstructive sleep apnea may improve while you are in this study but it may not. We expect that your symptoms will worsen (return to baseline) during the portion of the study in which your device is turned off.

This study is designed to learn more about the cardiovascular improvement with this form of treatment of obstructive sleep apnea. The study results may be used to help others in the future.

Information to be Collected

- Medical information about you including your medical history and present/past medications.
- Results of exams, procedures and tests you have before and during the study.

Specimens to be Collected

- Blood samples (before, during and after sleep apnea treatment)

Randomization and Blinding

There will be no randomization. Interpretation of all tests (sleep tests, ambulatory blood pressure monitoring, vascular test and blood tests) will single-blinded.

7. Data Sample Information

We will obtain a blood sample (about 1/2 cup) from you and store the blood for future analysis. The blood sample may be obtained by a nurse or physician as part of other blood draws you are undergoing during your visit(s). A study ID number will be used to link your blood sample to your other information. The DNA (genetic material) in your blood sample will be isolated and stored for future studies. Permanent cells may be created. Once DNA is isolated, it can be duplicated indefinitely for future research. Serum and plasma from your blood samples will also be stored and analyzed for a variety of biochemical factors. If you are less than 60 years old an extra tube of blood (about 1/2 tablespoon) will be collected. This extra tube of blood will be used to look at a special type of cell in your blood. This type of blood cell may help explain the difference between young women and young men with heart disease.

8. Community Participation

Not applicable

9. Participant Selection

Requested sample size: 50 subjects

Expected refusal/withdrawal: 10 subjects

Subjects completing study: 40 subjects

Inclusion criteria: All patients are English-speaking, greater than 18 years old and able to give informed consent. HGNS inclusion criteria per FDA require an AHI ≥ 20 on recent sleep testing, unable to use positive airway pressure therapy, BMI < 32 , without circumferential collapse on drug-induced sedated endoscopy. In essence, the inclusion criteria are those patients who have undergone HGNS implantation.

Exclusion criteria: active smokers, unstable and untreated coronary or peripheral artery disease, alpha-blockers, severe and inadequately controlled arterial hypertension.

Subject recruitment plan: All patients in the cohort will have undergone implantation of hypoglossal nerve stimulator by the principal investigator, [name], at the Sleep Surgery Center at Emory Midtown. At their 2-week post-operative appointment, they will be approached by the research coordinator at the Emory Sleep Center regarding participation in the study.

Screening for eligibility: Eligible subjects will be identified based on a clinical chart review by the principal investigator / surgeon, [name].

Procedures when a subject withdraws from the study:

1. Once the subject expresses that he/she would like to withdraw, no further information will be collected from the subject
2. Existing data will be utilized for appropriate analyses
3. These changes will be reflected in the intention-to-treat analysis

10. Informed Consent Process

The consent process will be done in person by the research assistant.

The research assistant will remain in the patient room for an extended period of time to ensure the subject's patients are adequately answered. We will deliberately schedule these patients as the last slot in the morning clinic allowing greater than 30 minutes before the first patient in the afternoon clinic. The research assistant will also ask the subject to repeat the procedures and timeline involved in this study.

The informed consent will allow for the subject to "opt out" of certain aspects of the study. The choices will be captured in the informed consent layout.

11. Incidental Findings

We anticipate incidental findings for the 24-hour blood pressure monitoring. We will set the following parameters for which the patient will be notified and asked to contact his/her primary care physician:

- Systolic BP > 200mm Hg for greater than 60 minutes of recording time
- Diastolic BP > 160mm Hg for greater than 60 minutes of recording time

The consent will include wording to indicate that he/she may be contacted if these results are seen. The principal investigator and treating physician ([name]) will call the patient to inform him/her of the findings. The subject will be provided the option to withdraw from the study at that time.

12. Compensation

The subject will not be offered payment for being in this study. However, we will provide mailing costs for return of sleep testing and blood pressure equipment. The subject will

also be provided lunch and parking vouchers for each time (3 in total) that he/she undergoes cardiovascular testing. The subject will not be responsible to pay for any cardiovascular testing as this is being done outside routine clinical care.

13. Statistical Analysis

With 40 subjects, we will have 89% power to detect a difference of 0.1 in the PAT ratio (primary outcome) with a standard deviation of 0.2 and alpha of 0.05.

Each subject will have a baseline PAT ratio derived from the average of the 10 obstructive events without stimulation (Aim 1). The PAT ratios at each stimulation level (5-7 stimulation levels based on previous experience) will be averaged from 5 obstructive events at each level. With greater than 30 data points per individual, linear regression will be performed for each subject with stimulation level as the main effect variable and PAT ratio as the outcome variable. We will determine if stimulation level is positively associated with PAT ratio. We will also perform linear regression, in a similar manner, from the combined values of the cohort to determine an effect at the sample level.

An interim analysis will not be performed as the primary outcome variable is largely observational (non-interventional); thus, the findings are expected during the treatment of moderate-severe obstructive sleep apnea

14. Data Safety and Monitoring Board

A DSMB will not be required. Access to this database will be restricted by a database manager and will be password protected. The only individuals who will be able to see patient identifiers, like name, address, and social security number, will be the Principal Investigator, research coordinators, recruiters and the database managers. Other investigators will have different passwords that will provide restricted access to the database. Those with restricted access will be able to query the database for scientific information/variables, but will not be able to view information on patient identifiers such as name, address, and social security number. If investigators with restricted access want to conduct studies which require them to obtain patient identifiers so that patients can be contacted for follow-up information/follow-up visits, these investigators will have to submit a separate protocol to IRB to get permission to obtain patient identifiers and contact patients.

15. Confidentiality

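### Baseline ambulatory blood pressure and baseline WatchPAT are recorded about two weeks after implant surgery, although the untreated window runs to Day 15 and would allow a later, more comparable baseline

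*Combined protocol and SAP*

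**What the plan says.** Section 9 (subject recruitment plan) states: "At their 2-week post-operative appointment, they will be approached by the research coordinator". The Study Timeline in Section 6 makes that visit the start of the study: "Post-operative appointment: obtain consent for study enrollment (Day 1".

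The baseline recordings then follow in two groups:

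- Early: "WatchPAT baseline home sleep test (Night 1" and "Baseline 24-hour ambulatory blood pressure monitoring (Day 2-3".
- Late: "Baseline serum biomarkers/vascular testing (Day 15", on the same day as "Device Activation (Day 15".

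At the two later time points, blood pressure is scheduled with the vascular and serum tests: "Treatment serum biomarkers/vascular testing, 24-hour ambulatory blood pressure monitoring (Day 105-106" and "Withdrawal serum biomarkers/vascular testing, 24-hour ambulatory blood pressure monitoring (Day 136-137".

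Section 6 states that there is no randomization, and the design is one cohort. The Aim 2c hypothesis (Section 5) has two parts: blood pressure improves on therapy, and after withdrawal it goes back to its pre-operative level. Section 4 states the second part as a return to baseline. No pre-operative recording is scheduled, and no reason is given for recording blood pressure on Day 2-3. Section 13 describes only the PAT-ratio analysis; it gives no method for ambulatory blood pressure and no adjustment for time since surgery.

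**The concern.** In a single-arm before-after comparison, whatever changes between the baseline and the treatment recording is counted in the treatment change. About two weeks after implantation, discomfort, disturbed sleep, altered activity or medication could still affect 24-hour blood pressure or a home sleep test. By Day 105 such effects would be expected to have gone.

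Two Aim 2c comparisons rest on the early baseline: the change from baseline to treatment, and the check that blood pressure returns to baseline after withdrawal. If surgery has left the baseline too high, the first is overstated and the second looks like an incomplete return. If surgery has left it too low, benefit is hidden. Since Section 13 plans no adjustment, the timing of the recording is the only protection, and the schedule leaves most of the untreated window unused.

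**Working it through.** **1. The plan's own figure.** The only power statement is in Section 13: 89% with 40 subjects, a difference of 0.1 in the PAT ratio, SD 0.2 and alpha 0.05. A paired two-sided normal approximation gives Φ(0.1/(0.2/√40) − 1.96) = Φ(3.162 − 1.960) = Φ(1.202) = 88.5%, which reproduces it to within rounding. (A paired t test gives 86.9%.) This figure concerns the PAT ratio and neither supports nor weakens the present point. No corresponding figure is given for blood pressure.

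**2. Time since surgery.** Taking the 2-week visit as post-operative day 14, post-operative day = 14 + study day − 1.

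| Recording | Study day | Post-operative day |
|---|---|---|
| Baseline WatchPAT | Night 1 | 14 |
| Baseline ambulatory BP | 2-3 | 15-16 |
| Baseline vascular and serum tests; activation | 15 | 28 |
| Treatment ambulatory BP | 105-106 | 118-119 |
| Withdrawal ambulatory BP | 136-137 | 149-150 |

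From the end of the baseline BP recording to activation is 15 − 3 = 12 days. From baseline to treatment BP is 105 − 2 = 103 days.

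**3. What a residual effect would do.** The documents give no figure for it, so it is expressed as an assumed shift in units of the SD of the paired change. With n = 40, a two-sided paired t test at 0.05 and no true device effect, the probability of a significant baseline-to-treatment result (noncentral t, noncentrality = shift × √40) is:

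| Assumed shift (SD) | Probability |
|---|---|
| 0 | 5% |
| 0.1 | 9% |
| 0.2 | 23% |
| 0.3 | 46% |
| 0.5 | 87% |

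The same table shows the opposite direction. A true benefit of 0.5 SD would be detected with 87% probability. If surgery had lowered the baseline by 0.2 SD, the visible change would be 0.3 SD and that probability would be 46%.

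**4. What a later recording would save.** Suppose the effect decays exponentially with half-life h. The fraction left after a delay of k days is 0.5^(k/h).

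| Assumed half-life | k = 10 | k = 11 | k = 12 |
|---|---|---|---|
| 3 days | 10% | 8% | 6% |
| 7 days | 37% | 34% | 30% |
| 14 days | 61% | 58% | 55% |

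Moving BP from Day 2-3 to Day 12-13 or Day 13-14 gives k = 10 or 11. Moving the WatchPAT from Night 1 to Night 11-13 gives k = 10 to 12. As an example, a 0.2 SD shift with k = 11 becomes 0.2 × 0.34 = 0.07 SD (7-day half-life) or 0.2 × 0.58 = 0.12 SD (14-day half-life). The 23% then falls to about 7% or 11%.

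**5. The withdrawal contrast.** Under the longest assumed half-life, the fraction of the baseline residual still present at treatment is 0.5^(103/14) = 0.6%. The treatment-versus-withdrawal comparison therefore carries almost none of it.

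**The case against.** The strongest reply is that the design already contains a safeguard. Recovery from surgery would not reverse when the device is switched off, so a fall from baseline followed by a rise on withdrawal could not come from recovery alone. The hypothesis predicts both movements, and a surgically raised baseline would count against the second. This stands for the treatment-versus-withdrawal contrast. It does not protect the size of the baseline-to-treatment change or the return-to-baseline test, and nothing in Section 13 prevents the first from being reported alone.

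Secondly, nothing in the documents shows that blood pressure is still altered at 15 days. That stands in full: size and direction are unknown, and if there is no residual effect there is no bias.

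Thirdly, some stronger readings are tempting but not supported:

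- A reader might take the gap of about 12 days between the BP baseline and the other Aim 2 baselines as a bias in itself. It is not. Aims 2a to 2d are separate hypotheses and no combined analysis is planned, so each measure can be compared with its own baseline. Only time since surgery matters.
- A reader might infer that the baseline BP is taken in a different setting. The documents describe 24-hour ambulatory monitoring at all three time points and no difference in setting.
- A reader might expect that moving the WatchPAT would align it with the vascular tests as at the later time points. At treatment it is on Night 75, about 30 days before Day 105, so no such pairing holds there.
- A reader might extend the point to the primary outcome. Section 13 does not say which recording supplies the unstimulated events for the baseline PAT ratio, so the documents do not establish this.

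**Conclusion.** The dates are firm: the baseline WatchPAT and ambulatory BP are taken about 14 to 16 days after surgery, with the device off until about post-operative day 28 and no reason given for recording early. Because there is no control group, the Aim 2c baseline-to-treatment change and the return-to-baseline test are open to any residual post-operative effect, in either direction. The treatment-versus-withdrawal contrast is largely protected.

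The documents do not support saying that the trial will show a false improvement, or attaching a number of mmHg to the bias. The probabilities above rest on assumed shifts, and the gain from waiting rests on assumed half-lives: about 39 to 42% of any residual BP effect removed with a 14-day half-life, 63 to 66% with 7 days. Ambulatory BP is also not the primary outcome. This is a worthwhile, low-cost improvement to a secondary aim rather than a flaw that undermines the study.

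**What to change.** 1. In the Study Timeline, move both baseline recordings to the last days before activation, for example WatchPAT on about Night 11-13 and ambulatory BP within Day 12-14, finished before the Day 15 vascular visit and activation. They would then fall on about post-operative days 24 to 27. The activation date is not touched.
2. State that the equipment is issued on Day 1 or mailed.
3. In the Aim 2 hypotheses, replace the pre-operative reference level with a pre-activation baseline. Even the moved recordings, and the vascular and serum baselines on Day 15, are only about four weeks post-operative, and no pre-operative measurement exists to compare with.
4. In Section 13, state that for ambulatory BP the treatment-versus-withdrawal contrast will be reported alongside baseline versus treatment.

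The cost is a protocol amendment with the same number of recordings. The downsides are less time to repeat a failed recording before activation, and slightly more equipment handling, since devices must be held for longer after Day 1 or sent out. The change reduces the exposure without removing it, which is why items 3 and 4 are needed as well.

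### The baseline 24-hour blood pressure recording is made away from the fasting blood and vascular visit, while the treatment and withdrawal recordings share its two-day window, so the Aim 2c comparisons with baseline are not like for like

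*Combined protocol and SAP*

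**What the plan says.** The Study Timeline in Section 6 separates the two baseline assessments: "Baseline 24-hour ambulatory blood pressure monitoring (Day 2-3") and "Baseline serum biomarkers/vascular testing (Day 15"). In the two later periods they share one line and one two-day window: "Treatment serum biomarkers/vascular testing, 24-hour ambulatory blood pressure monitoring (Day 105-106") and "Withdrawal serum biomarkers/vascular testing, 24-hour ambulatory blood pressure monitoring (Day 136-137"). The treatment window also holds a further appointment: "Clinic visit (Day 105").

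Section 6 describes what the blood and vascular visit involves. "Each set of testing will require travel to the Emory Clinical Cardiovascular Research Institute (ECCRI) facility", where participants "undergo fasting bloodwork". Under Risks, the vascular test is described: "The blood pressure inflation lasts for 5 minutes and can result in temporary feelings of numbness and pins and needles in the arm". Section 7 puts the blood sample at roughly half a cup.

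Aim 2c (Section 5) predicts that 24-hour blood pressure improves on therapeutic stimulation and goes back to its earlier level after 30 days off. Section 5 therefore makes two comparisons with baseline. Section 6 states that there is no randomization, and there is no control group. Section 13 describes analyses of the PAT ratio only. It contains no analysis for Aim 2c and nothing on recording conditions.

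**The concern.** A before-during-after comparison within subjects is only as good as the sameness of the measuring conditions. Here the conditions change at the same point as the treatment. The baseline recording falls on days with no other study procedure listed. A 24-hour recording inside Day 105-106 or Day 136-137 needs both days of the window, so it must overlap the visit or directly precede or follow it.

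If travel, fasting, the blood draw or the testing moves the 24-hour mean at all, the movement is present in both later recordings and absent at baseline. With no control group, a comparison with baseline cannot separate it from the effect of stimulation.

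At stake is the reading of Aim 2c. A downward shift would look like improvement, followed by a failure to return. An upward shift would hide a real improvement.

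**Working it through.** **The plan's own figure.** The only power figure is for the PAT ratio (Section 13: 40 subjects, difference 0.1, SD 0.2, alpha 0.05, 89%). Treating 0.2 as the SD of the paired difference, 0.1 / (0.2/√40) = 3.162, and Φ(3.162 − 1.960) = 0.885, which rounds to 89%. It reproduces but says nothing about blood pressure. The documents give no blood pressure SD, target difference or test.

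**Timing, from the Study Timeline.**

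| Period | 24-hour recording | Blood/vascular testing | Gap |
|---|---|---|---|
| Baseline | Day 2-3 | Day 15 | 12-13 days |
| Treatment | Day 105-106 | Day 105-106 | same window |
| Withdrawal | Day 136-137 | Day 136-137 | same window |

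**Where a visit-day shift goes.** Let m be the untreated mean, τ the effect of stimulation, and b the visit-day shift in the 24-hour mean, with full washout after withdrawal.

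- Baseline = m; treatment = m + τ + b; withdrawal = m + b.
- Treatment minus baseline = τ + b.
- Withdrawal minus baseline = b.
- Treatment minus withdrawal = τ.

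The first two differences are the ones in the Aim 2c hypothesis, and both carry b in full. The third is free of b, provided the shift is the same in both later periods. The Day 105 clinic visit, which has no counterpart at withdrawal, is a small reservation.

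**Illustration of size (assumed inputs).** Take n = 40 completers (Section 9), a two-sided 5% paired t-test (39 df, critical value 2.023), τ = 0, and an assumed SD of change of 8, 10 or 12 mmHg. The standard error is SD/√40 and the noncentrality is b divided by it. The cells give the chance of a significant change from baseline.

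| SD | SE | b = 0 | b = 1 mmHg | b = 2 mmHg |
|---|---|---|---|---|
| 8 | 1.26 | 5% | 12.0% | 33.8% |
| 10 | 1.58 | 5% | 9.5% | 23.5% |
| 12 | 1.90 | 5% | 8.1% | 17.7% |

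Almost all of these rejections are in the direction of the shift. At SD 10 and b = +2, less than 0.1 percentage point of the 23.5% is in the direction of improvement.

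**Masking.** With an assumed true effect of −5 mmHg and SD 10, the power for treatment versus baseline is 87% at b = 0, 46% at b = +2 and 99% at b = −2.

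**The case against.** The strongest reply is that no visit-day effect is shown. The timeline gives days, not hours. If the monitor is fitted after testing, the outward journey, the fast and the cuff occlusion fall outside the recording. The protocol provides lunch at each visit and describes the cuff sensations as lasting a minute or two. All of this stands: b may be zero, and every mmHg figure above rests on assumptions. What remains is that the protocol does not fix the order, and that even a recording started after testing begins on a visit day, which the baseline recording does not.

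Three stronger readings are tempting, and the documents do not support them.

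- A reader might infer that the schedule could produce false confirmation of Aim 2c. It would not do so by itself. With no true effect, a negative b gives apparent improvement, no return to baseline, and no difference between treatment and withdrawal. That contradicts the hypothesised pattern.
- A reader might infer that a positive shift exaggerates the rebound when therapy stops. The change from treatment to withdrawal is exactly where b cancels. Only the comparison of withdrawal with baseline is raised.
- A reader might take a larger shift and quote a larger error rate; at 3 mmHg the same calculation gives 34-64%. A 3 mmHg shift in the 24-hour mean needs, for example, a 10 mmHg difference lasting 7.2 hours (10 × 7.2 / 24 = 3). Differences of 5 mmHg over 4 hours and 5 mmHg over 8 hours give 0.83 and 1.67 mmHg. Nothing in the documents points to the upper end.

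It is also fair to say that Aim 2c is not the primary outcome, and that the lack of any written Aim 2c analysis is the more basic gap. Both points lower the severity, but neither removes the mismatch.

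**Conclusion.** The point holds as a minor, avoidable confound. The difference in recording conditions between baseline and the two later periods is plain in the current timeline. It follows by algebra that any visit-day shift enters both comparisons with baseline in full and cancels in treatment minus withdrawal. Nothing in Section 13 removes it.

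It is not a demonstrated bias, because the size, the sign and the within-window order are all unstated. The illustrative rates (5%, 8-12% and 18-34% for shifts of 0, 1 and 2 mmHg) depend on an assumed SD of change of 8-12 mmHg and an assumed paired t-test with 40 completers. They count as false improvement only if the shift is negative. That Aim 2c will be analysed as change from baseline is itself inferred from its hypothesis.

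**What to change.** In the Study Timeline, give all three 24-hour recordings the same stated relation to the blood and vascular visit. One way is to complete each recording immediately before that period's testing. The baseline recording would move next to the Day 15 visit and finish before device activation. The later recordings can stay in their present windows, which keeps the full 30-day off period and leaves the withdrawal recording after its WatchPAT night. State also how the treatment recording is placed relative to the Day 105 clinic visit.

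At the same time, reconcile two overlaps. The Day 105-106 recording shares Day 106 with the start of therapy withdrawal, and the Day 136-137 recording shares Day 137 with therapy reactivation. The text should make clear what the device status is during each recording.

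If the calendar cannot move, Section 13 should:

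- name treatment versus withdrawal as the like-for-like Aim 2c contrast;
- report change from baseline as supportive, with the difference in conditions stated;
- add a sensitivity analysis that drops the same visit-day clock hours from all three recordings, which requires fitting and testing times to be recorded.

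The cost is a timeline amendment and a separate hand-out of the monitor before the baseline visit. The same may be needed before the withdrawal visit if the monitor is now fitted there. Section 12 covers postage for returning equipment but does not mention sending it out. The baseline recording would also no longer come directly after a WatchPAT night, as the withdrawal one does. No test or patient is added. The fallback costs some wording and a small amount of extra analysis, but it leaves the return to the earlier level without a like-for-like comparison.
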